7.1. Adverse Events

Adverse events (AEs) will be coded using the Medical Dictionary for Regulatory Activities (MedDRA) version 26.0 or more recent version (at the time of database lock) and graded according to NCI-CTCAE version 5. All laboratory test results will be classified for toxicity grade according to the NCI-CTCAE version 5 criteria.

DLTs will be listed and summarized based on the DLT Evaluable Population.

Treatment emergent adverse events (TEAEs) are those events that occur or worsen on or after the first dose of study drug up through 30 days post the last dose. Those events occurred after start of subsequent anticancer therapy will be excluded.

An overview summary table of the number and percentage of patients in each of the categories listed below will be presented. This summary will be presented based on all patients in the study (overall summary to summarize unique patients) and then repeated split by module 1a or 1b and dose/schedule (see Section 5.1 for general presentation format).

- All TEAEs
- Treatment related TEAEs (related to either study drug)
- DLTs
- TEAEs with \geq CTCAE Grade 3
- Treatment-related TEAEs with \geq CTCAE Grade 3 (related to either study drug)
- Serious TEAEs
- Treatment-related serious TEAEs (related to either study drug)
- TEAEs with outcome of death
- TEAEs leading to discontinuation of study treatment
- TEAEs leading to dose modification (i.e., dose reduced or dose interrupted) of study treatment

TEAEs will be summarized by system organ class (SOC), preferred term (PT), and by NCI CTCAE toxicity grade (where applicable). For summary tables, an AE that occurs more than once within a SOC and/or PT for the same patient will be counted only once using the worst NCI toxicity grade experienced.

Number and percentage of participants with TEAEs will also be presented by PT only. This summary will be sorted in decreasing order of frequency based on overall safety population.

For the summary tables related to toxicity grades, if there are two or more TEAEs (or AEs) with same SOC or PT and different toxicity CTCAE grades for the same subject, only the maximum toxicity grade of AE be counted.

Data listing will be provided for all TEAEs, TEAEs with ≥ CTCAE Grade 3 and serious TEAEs.

An AE table of most frequently occurring TEAEs, showing all events in at least 5% of patients, will be summarized by preferred term, by decreasing frequency based on all patients. This cut-off may be modified after review of the data.

TEAEs with outcome of death, leading to discontinuation of study treatment or leading to dose reduction, dose interruption or discontinuation of study treatment will be summarized by preferred term. Corresponding listings will be provided. If the number of occurrences is low (e.g., when \leq 5 patients involved), only listing will be provided. If necessary, tabulated by preferred term depending on the number of TEAEs reported for those categories.

For patients who have a dose modification, all AEs (due to drug or otherwise) will be assigned to the initial dose group for summarizing. Any AE occurring before the first dose of study treatment will be included in the data listings but will not be included in the summary tables of AEs.

Summary tables will include only treatment-emergent adverse events (TEAEs). Non-TEAEs will be listed but will not be included in the summaries. Note that those events with onset after start of subsequent anticancer therapy will be excluded from the TEAE summary.

Pooled rash will include preferred terms of Rash Maculo-popular, Pruritis, Rash, Skin Exfoliation, Erythema, Dermatitis Contact, Eczema, Flushing, Rash Erythematous, and Rash Pruritic.

A listing of all deaths and causes of deaths will be provided.

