1. SYNOPSIS

Name of Sponsor/Company: Repare Therapeutics

Name of Investigational Products: RP-6306, [Folinic Acid (Leucovorin), Fluorouracil, Irinotecan] (FOLFIRI)

Name of Active Ingredients: RP-6306, [Folinic Acid (Leucovorin), Fluorouracil, Irinotecan] (FOLFIRI)

[figure not shown]
Title of Study: Phase 1 Study of the PKMYT1 Inhibitor RP-6306 in Combination with FOLFIRI for the Treatment of Advanced Solid Tumors (**MINOTAUR** Study: PKMYT1 INhibitor and FOLFIRI TreAtment of Solid Tumors)

Study Duration: Approximately 30 months Phase of Development: 1

Number of Patients (planned): Up to 104 evaluable patients are planned to be enrolled in this study.

Objectives and Endpoints:

Primary Objectives	Primary Endpoints
To assess the safety and tolerability of RP-6306 in combination with FOLFIRI in patients with eligible, advanced solid tumors	Incidence and severity of treatment-emergent adverse events (TEAEs), laboratory assessments, vital signs, electrocardiograms (ECGs), and use of concomitant medications
To define the maximum tolerated dose (MTD) and the recommended Phase 2 dose (RP2D) and schedule of RP-6306 in combination with FOLFIRI	Dose-limiting toxicities (DLTs)
Secondary Objectives	Secondary Endpoints
To assess the preliminary efficacy of RP-6306 in combination with FOLFIRI in patients with molecularly selected, advanced solid tumors	Best percent change in tumor size from baseline, objective response rate (ORR), best overall response rate, duration of response (DOR), clinical benefit rate (CBR), progression-free survival (PFS) at 6 months, and overall survival (OS) at 12 months
To assess PK parameters of RP-6306 in combination with FOLFIRI	Plasma concentrations of RP-6306, irinotecan, and SN-38 with calculation of maximum observed plasma concentration within the dosing interval (C _{max}), time to maximum observed plasma concentration (T _{max}), area under the plasma concentration-time curve from time 0 to t ("t" being the longest time interval evaluable in all periods) (AUC _{0-last}), and other parameters as appropriate
Exploratory Objectives	Exploratory Endpoints

Study Design:

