Patients will continue treatment until disease progression by RECIST v1.1, AE, Investigator decision, withdrawal of consent, protocol noncompliance, pregnancy, or death. After treatment discontinuation, patients will be followed for survival. Survival Follow-up assessments will be done via telephone (or standard method used by participating centers as agreed upon by the Sponsor) every 3 months (±2 weeks) up to 12 months unless the patient withdraws consent to the study, the study is terminated, the patient dies or is LTFU.

Safety:

All AEs/SAEs in enrolled patients must be recorded regardless of the relationship of the AE/SAE to the study treatment from the date of first dose of study treatment through 30 days after the last dose of study treatment, or the start of new anticancer treatment if earlier than 30 days. SAEs considered related to study treatment are to be reported until the end of the Survival Follow-up Period which is up to 12 months after the last dose of investigational product (IP) or until LTFU, patient withdrawal of consent, or whenever the investigator becomes aware thereafter.

During the Screening Period, all AEs related to study procedures are to be captured from the time ICF is signed to the first dose of study treatment. AEs considered not related to study procedures occurring during the Screening Period are to be captured as medical history.

All AEs experienced by a patient, irrespective of the suspected causality, will be monitored and recorded until the TEAE or SAE has resolved; abnormal laboratory values have normalized, stabilized, or returned to baseline and there is a satisfactory explanation for the changes observed; withdrawal of consent; or the patient is LTFU or has died. Any AE that occurs beyond the reporting period that the Investigator assesses as at least possibly related to RP-6306 and/or FOLFIRI should be reported to Repare Therapeutics.

Tolerability and safety will be evaluated by assessment of AEs, TEAEs, SAEs, DLTs, concomitant medications, PEs, vital signs, clinical safety laboratory evaluations (hematology, chemistry, and urinalysis), ECOG performance status, ECGs, and exposure (including dose interruptions and modification).

Concomitant Medications:

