The efficacy analysis will be summarized by dose combination and data from the backfill cohorts will be pooled with patients from the Dose Finding Phase that were treated at the RP2D (a minimum of 6 patients are expected to be treated at the RP2D during dose finding) when applicable.

Each cohort will be evaluated for ORR, best overall response rate, CBR, DOR, changes in tumor size, PFS at 6 months, and any available OS at 12 months.

Safety Analysis:

Toxicity will be summarized by grade and type. All AEs will be listed, including the verbatim description, system organ class, and preferred term.

Incidence of TEAEs, treatment-related TEAEs, TEAEs leading to death, SAEs, treatment-related SAEs, TEAEs leading to study treatment discontinuation or interruption, and TEAEs leading to dose modifications will be recorded. Clinically relevant laboratory abnormalities (ie, laboratory abnormalities that result in treatment modification or require intervention) will be recorded as AEs. TEAEs will be further summarized by severity (according to NCI CTCAE version 5.0). Changes in clinical laboratory parameters (eg, hematology, chemistry, urinalysis, etc.), CTCAE graded laboratory toxicities, vital signs, ECOG performance status, PEs, and usage of concomitant medications and procedures will be summarized.

PK Analysis:

PK parameters for RP-6306, irinotecan, and SN-38 will be calculated using noncompartmental analysis or other modeling methods as well as using a population PK model: AUC_{0-last} , C_{max} , and T_{max} , and other parameters as appropriate.

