2. STUDY OBJECTIVES AND ENDPOINTS

2.1. Module 1 Objectives and Endpoints

Primary Objectives	Primary Endpoints
To assess the safety and tolerability of RP-6306 in combination with FOLFIRI in patients with eligible, advanced solid tumors	Incidence and severity of treatment-emergent adverse events (TEAEs), laboratory assessments, vital signs, electrocardiograms (ECGs), and use of concomitant medications
To define the maximum tolerated dose (MTD) and the recommended Phase 2 dose (RP2D) and schedule of RP-6306 in combination with FOLFIRI	Dose-limiting toxicities (DLTs)
Secondary Objectives	Secondary Endpoints
To assess the preliminary efficacy of RP-6306 in combination with FOLFIRI in patients with molecularly selected, advanced solid tumors	Best percent change in tumor size from baseline, objective response rate (ORR), best overall response rate, duration of response (DOR), clinical benefit rate (CBR), and progression-free survival (PFS) at 6 months
To assess PK parameters of RP-6306 in combination with FOLFIRI	Plasma concentrations of RP-6306, irinotecan, and SN-38 with calculation of maximum observed plasma concentration within the dosing interval (C_{max}), time to maximum observed plasma concentration (T_{max}), area under the plasma concentration-time curve from time 0 to t ("t" being the longest time interval evaluable in all periods) (AUC _{0-last}), and other parameters as appropriate

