2.2.1. Safety Endpoints

- DLTs
- Incidence of TEAEs, treatment related TEAEs, TEAEs leading to death, serious adverse events (SAEs), treatment related SAEs, TEAEs leading to study drug discontinuation, TEAEs leading to dose modifications (interruptions or reductions)
- Changes in clinical laboratory parameters (hematology, chemistry, urinalysis), CTCAE graded laboratory toxicities, vital signs, Eastern Cooperative Oncology Group (ECOG) performance status, ECG parameters including QTc, physical exams (PEs) and usage of concomitant medications

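### Treatment-related SAEs are listed as a safety endpoint without a time limit and collected for up to 12 months, but the SAP tabulates only those that qualify as TEAEs

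*SAP*

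**What the plan says.** **Endpoint lists.** SAP 2.2.1 includes "serious adverse events (SAEs), treatment related SAEs" among the safety endpoints whose incidence is to be reported. The Safety Analysis paragraph of the protocol synopsis has a parallel list: "Incidence of TEAEs, treatment-related TEAEs, TEAEs leading to death, SAEs, treatment-related SAEs". In both lists the items for death, discontinuation and dose modification are qualified as TEAEs. The SAE items are not.

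**Collection.** The Safety paragraph of the protocol synopsis records AEs and SAEs of any cause to 30 days after the last dose, or to new anticancer treatment if that comes sooner. It sets a longer period for one class: "SAEs considered related to study treatment are to be reported until the end of the Survival Follow-up Period". That period is up to 12 months after the last dose, and the duty continues if the investigator learns of an event later.

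**Tabulation.** SAP 7.1 defines TEAEs as events from first dose to 30 days after the last dose and excludes those arising after subsequent anticancer therapy. Its overview table has rows for serious TEAEs and for "Treatment-related serious TEAEs (related to either study drug". It limits summary tables to TEAEs and adds: "Non-TEAEs will be listed but will not be included in the summaries".

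**Primary endpoint.** The endpoint table of the protocol synopsis gives "Incidence and severity of treatment-emergent adverse events (TEAEs), laboratory assessments, vital signs, electrocardiograms (ECGs), and use of concomitant medications", and SAP 2.1 repeats it. The protocol's TEAE definition, under Dose-Limiting Toxicity Criteria, ends at 30 days after the last dose and has no cut at new therapy.

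**The concern.** The trial extends collection for one class of event, related SAEs, and names their incidence among its safety endpoints. The SAP then has no table in which the later ones can be counted. A reader of the study report would find a related-SAE percentage by dose level and could reasonably take it as the rate for the listed endpoint, although it covers a narrower set of events.

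The error can go only one way. The denominator, the Safety Population, is the same under either definition, and the tabulated events are a subset of those collected. SAP 3.2.2 bases the RP2D on the totality of safety, PK, pharmacodynamic and preliminary efficacy data. Dose-level groups may be small, so a single omitted patient can visibly change a percentage that feeds that judgement.

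**Working it through.** The plan states no figure for this point, and no sample size, power or alpha depends on it. The check is a comparison of definitions, followed by the weight of one patient.

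**Step 1: follow three related SAEs through the documents.** Days are counted from the last dose.

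| Related SAE | Collected (protocol, Safety) | TEAE by protocol definition | In the SAE items of SAP 2.2.1 | In a SAP 7.1 table |
|---|---|---|---|---|
| Day 10, no new therapy | Yes | Yes | Yes | Yes |
| Day 20, new therapy from day 15 | Yes | Yes | Yes | No |
| Day 35, no new therapy | Yes | No | Yes | No |

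The second event is lost both from the related-SAE incidence and from TEAE incidence as the protocol defines it. The third is lost from the related-SAE incidence only.

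**Step 2: check the general SAE item.** An unrelated SAE on day 35, or after new therapy, falls outside the protocol's collection period for events of any cause. The gap is therefore confined to related SAEs.

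**Step 3: share of the collection period that can be tabulated.** 30 / 365.25 = 8.2% of the 12 months after the last dose; the other 91.8% can reach listings only. This is a share of time. It says nothing about the share of events, which may well cluster early.

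**Step 4: weight of one omitted patient, 100/n.**
- n = 104 (maximum total, SAP 3.3): 100/104 = 0.96 percentage points.
- n = 40 (maximum per module, SAP 3.3): 100/40 = 2.5 points.
- n = 6 (minimum expected at the RP2D during dose finding, SAP 8): 100/6 = 16.7 points.

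**Step 5: chance that at least one patient is affected.** The documents give no late-SAE rate, so the per-patient risk q is an assumption, shown over a range. The chance is 1 − (1 − q)^104, and the expected number of patients is 104 × q.

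| Assumed q | Expected patients among 104 | Chance of at least one |
|---|---|---|
| 0.5% | 0.5 | 41% |
| 1% | 1.0 | 65% |
| 2% | 2.1 | 88% |
| 5% | 5.2 | 99.5% |

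**The case against.** A reader might infer that late related SAEs drop out of the primary safety incidence. For events after day 30 the documents do not support that. The primary endpoint in both documents is TEAE incidence, and such an event is not a TEAE under either definition. It was never in the primary incidence.

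A reader might also infer that these events disappear from the report. They do not. SAP 7.1 lists non-TEAEs and all deaths, and SAP 5.2.1 puts all recorded data in listings. What is missing is a count by dose level. The dedicated serious-event listing in SAP 7.1 is itself restricted to serious TEAEs, so late related SAEs would sit among the general non-TEAEs.

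The stronger objections concern the endpoint and the remedy:

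- **The protocol does not call these items endpoints.** Its Safety Analysis paragraph says their incidence will be recorded; only SAP 2.2.1 uses the endpoint heading. That stands, but it makes the mismatch internal to the SAP, between 2.2.1 and 7.1.
- **SAP 2.2.1 could be read as meaning serious TEAEs.** This is possible, but the same sentence attaches the TEAE qualifier to its neighbours and leaves it off the SAE items.
- **The cut at new therapy follows the protocol.** It does for events of any cause. It does not for related SAEs, which the protocol goes on collecting.
- **A reporting duty is not an analysis window.** Survival Follow-up is by telephone or a site's standard method every 3 months, so late events are found less reliably and over unequal follow-up. This stands. It is a reason to keep the late count in its own labelled row.
- **Listings suffice for small numbers.** SAP 7.1 allows listing only when about 5 or fewer patients have certain outcomes (death, discontinuation, dose changes). Those categories still have rows in the overview table. Late related SAEs have none.

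**Conclusion.** The point holds as a mismatch between a listed safety endpoint and its planned summary. Under SAP 7.1 the tabulated related-SAE incidence can only equal or understate the incidence listed in SAP 2.2.1 and in the protocol's Safety Analysis. The primary TEAE endpoint is touched in one narrow case: a related SAE within 30 days of the last dose but after new anticancer therapy is a TEAE under the protocol definition, and the SAP removes it.

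The size is unknown. One patient moves the rate by 0.96 points at n=104 and by 16.7 points at n=6. The probabilities in the working rest on assumed risks and show only that an affected patient is plausible. DLT-based MTD finding uses the first 28 days and does not depend on this row. Severity: minor.

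The conclusion assumes that the unqualified SAE items are to be read as written, and that related SAEs are in fact recorded through Survival Follow-up as the protocol requires.

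**What to change.** In SAP 7.1, add to the overview table, by dose level, a separate row: *Treatment-related SAEs at any time from first dose to end of Survival Follow-up*. Count related SAEs there regardless of the 30-day limit and of subsequent therapy. Keep the serious-TEAE rows unchanged beside it. Add a footnote that late events are ascertained less intensively and over unequal follow-up. Exempt this row from the sentence that keeps non-TEAEs out of the summaries.

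Rewording SAP 2.2.1 to say that SAEs means serious TEAEs would remove the inconsistency within the SAP. It would still leave the late related SAEs without an incidence and would not address those lost at the start of new therapy.

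The cost is one extra row from data already collected, and a stated related-SAE rate that may be slightly higher. No sample size or dose rule changes.

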This study aims to identify the RP2D and preferred dosing schedule of RP-6306 in combination with FOLFIRI. The DLT evaluation period will consist of 2 cycles (28 days) of treatment. Initially, RP-6306 will be given on a continuous, once daily (QD) schedule (Module 1a) with dose escalation and de-escalation decisions guided by the BOIN drug combination criteria. If necessary, an intermittent dosing schedule (Module 1b) of 3 consecutive days on / 4 consecutive days off may be explored, and Module 1a may be terminated or proceed concurrently with Module 1b. Escalation/de-escalation will proceed independently as guided by the BOIN drug combination criteria. If both modules are run concurrently, patients will be enrolled into either Module 1a or 1b based on available slot openings at the time of signing the ICF and allocated to a cohort by the Medical Monitor with guidance from the SRC.

Module 1a:

The study will start at Dose Level 1 with up to 2 patients receiving 40 mg QD, oral RP-6306 in combination with 180 mg/m² IV irinotecan given over 30 to 90 minutes, 400 mg/m² IV leucovorin given over 30 to 90 minutes with irinotecan, and 400 mg/m² IV fluorouracil bolus after leucovorin, then 2400 mg/m² IV continuous IV of fluorouracil over 46 hours (Days 1 and 2) of each 14-day cycle.

This dose of RP-6306 was chosen based on the observed tolerability and PK of RP-6306 monotherapy in the MYTHIC study. If Dose Level 1 is tolerated, the dose of RP-6306 will be escalated to 120 mg and the dose of irinotecan will be maintained at 180 mg/m² daily (Dose level 2). In addition, patients treated at Dose Level 1 will be eligible to receive RP-6306 at 120 mg QD, if Dose Level 2 has completed the DLT evaluation period and if agreed upon by the SRC. If Dose Level 1 is not tolerated, the dose of irinotecan will be de-escalated to 150 mg/m² and RP-6306 will be maintained at 40 mg daily (Dose level 1D).

After Dose Level 2, dose escalation of RP-6306 will proceed to the next higher dose level following BOIN criteria and dose escalation and de-escalation rules as follows:

- Dose escalation will progress with N≥2 patients with increases of up to 100% RP-6306 until a
 DLT is observed (Level R in Figure B and Table A below). Dose decisions will depend on 2 or
 more evaluable patients completing the first 2 14-day treatment cycles.

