3.2.1. Dose and Schedule Finding

This study aims to identify the RP2D and preferred dosing schedule of RP-6306 in combination with FOLFIRI. RP-6306 will be given on a continuous QD schedule (Module 1a) and intermittent schedule

(Module 1b) as outlined below. If both modules are run concurrently, patients will be enrolled into either Module 1a or 1b based on available slot openings at the time of signing the ICF and allocated to a cohort by the Medical Monitor with guidance from the SRC.

Module 1a

The study will start at Dose Level 1 with up to 2 patients receiving 40 mg QD, oral RP 6306 in combination with 180 mg/m2 IV irinotecan given over 30 to 90 minutes, 400 mg/m2 IV leucovorin given over 30 to 90 minutes with irinotecan, and 400 mg/m2 IV fluorouracil bolus after leucovorin, then 2400 mg/m2 IV continuous IV of fluorouracil over 46 hours (Days 1 and 2) of each 14 day cycle.

This dose of RP-6306 was chosen based on the observed tolerability and PK of RP-6306 monotherapy in the MYTHIC study. If Dose Level 1 is tolerated, the dose of RP 6306 will be escalated to 120 mg and the dose of irinotecan will be maintained at 180 mg/m2 daily (Dose level 2). In addition, patients treated at Dose Level 1 will be eligible to receive RP-6306 at 120 mg QD, if Dose Level 2 has completed the DLT evaluation period and if agreed upon by the SRC. If Dose Level 1 is not tolerated, the dose of irinotecan will be de-escalated to 150 mg/m2 and RP 6306 will be maintained at 40 mg daily (Dose level 1D).

After Dose Level 2, dose escalation of RP-6306 will proceed to the next higher dose level following BOIN criteria and dose escalation and de-escalation rules as follows:

- Dose escalation will progress with N≥2 patients with increases of up to 100% RP 6306 until a DLT is observed (Level R in Figure 3 and Table 1 below). Dose decisions will depend on 2 or more evaluable patients completing the first 2 14-day treatment cycles.
- For de escalation at Level R and thereafter, the next dose level of RP 6306 will be ≥25% lower than the current dose (rounded down based on capsule strength) or de-escalated down to the highest previously tolerated dose based on review of the toxicity patterns by the SRC. In addition to decreasing the daily dose level of RP 6306, de-escalation can involve a reduced frequency of dosing (eg, 3 consecutive days on / 4 consecutive days off or 1 week on / 1 week off).

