- Dose escalation of RP-6306 will follow the BOIN criteria as guided by the SRC. RP 6306 can continue with increases of 20% to 50% (R+1).

Module 1b

[figure not shown]
If tolerability of continuous RP-6306 with FOLFIRI is limiting, Module 1b will be initiated if agreed upon by the SRC. In Module 1b, an intermittent dosing schedule of RP-6306 given 3 consecutive days on / 4 consecutive days off will be tested in combination with FOLFIRI. When Module 1b is initiated, the starting dose of RP-6306 and FOLFIRI will be the same as the highest total daily dose evaluated in Module 1a and will be given to a cohort of N≥2 patients. To allow better dose and schedule exploration early in the development, additional schedules may be evaluated that involve intermittent dosing (eg, 2 consecutive days on / 5 consecutive days off or 1 week on / 1 week off) depending on observed toxicities. The dose of RP-6306 or FOLFIRI will be increased or decreased per BOIN criteria independently of Module 1a until an MTD is established. Dose escalation decisions will be discussed with the SRC after at least 2 evaluable patients completing the first 2 14-day treatment cycles and based on the emerging safety and tolerability profile, and clinical PK/pharmacodynamic data across the entire patient population in Modules 1a and 1b.

In the event Modules 1a and 1b are explored concurrently, the Medical Monitor and SRC will prioritize slot allocation for each module. The highest dose level of RP-6306 in this study will not exceed the MTD

of RP-6306 monotherapy identified in the MYTHIC study for a given schedule. The totality of safety, PK, pharmacodynamic, and preliminary efficacy data will be used to select a preferred RP2D and schedule for RP-6306 and FOLFIRI.

If anti-tumor activity is observed at a dose level that is lower than the current dose level being explored (after escalation has proceeded to a higher dose level), additional patients (N≤6), preferably with the same tumor/genomic alteration, may be enrolled at the lower dose level to further confirm safety and efficacy at that dose level. The relevant DLTs from the backfill cohorts will be included in the MTD and RP2D determination by the SRC. Additionally, intrapatient dose escalations for patients at a lower dose level will be allowed at the discretion of the Investigator, and with Sponsor approval and guidance by the SRC, if the higher dose level was deemed safe by the SRC.

Figure 3: Module 1a and 1b Escalation Schema

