4.3. Safety Population

The **Safety Population**, used for the assessment of overall safety and tolerability, will consist of all patients who receive at least one dose of study treatment. Patients will be assessed for safety based on the dose level in which they are enrolled.

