4.4. Pharmacokinetic Population

The **Pharmacokinetic Population**, used for the assessment of PK endpoints, will consist of all patients who have sufficient RP-6306, irinotecan and/or SN-38 PK concentration data recorded to derive PK endpoints.

For all analysis populations, patients will be presented by the initial dose received.

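### By-dose safety and efficacy tables use the starting dose although patients may escalate, so events and responses arising after escalation appear under the lower dose

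*SAP*

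**What the plan says.** **Grouping.** SAP 4.3 states: "Patients will be assessed for safety based on the dose level in which they are enrolled". The closing sentence of SAP 4.4 is broader: "For all analysis populations, patients will be presented by the initial dose received". SAP 5.1 presents safety and efficacy by assigned dose/schedule, and DLT rates by assigned initial dose level. For patients with a dose modification, SAP 7.1 says that "all AEs (due to drug or otherwise) will be assigned to the initial dose group for summarizing".

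**Escalation.** The first cohort is small: "The study will start at Dose Level 1 with up to 2 patients receiving 40 mg QD" (SAP 3.2.1). The Protocol Synopsis (Module 1a) provides that "patients treated at Dose Level 1 will be eligible to receive RP-6306 at 120 mg QD", on the condition that SAP 3.2.1 repeats: "if Dose Level 2 has completed the DLT evaluation period and if agreed upon by the SRC". A general provision follows: "intrapatient dose escalations for patients at a lower dose level will be allowed at the discretion of the Investigator", with Sponsor approval and SRC guidance. The Synopsis section on investigational product and dosage extends this to RP-6306, irinotecan or both.

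**Reporting.** TEAEs run from first dose to 30 days after the last dose, and only the worst grade per term is counted (SAP 7.1). SAP 7.2 reports the number of patients with any escalation. For FOLFIRI it lists only duration and number of infusions.

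**The concern.** A patient who escalates contributes time at two or more doses, but the by-dose tables have one column for that patient: the starting dose. No planned table shows events by dose at onset, and no flag separates events or responses that arose after escalation.

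The RP2D may be the MTD or a lower dose, chosen on the totality of safety, PK, pharmacodynamic and efficacy data (SAP 3.2.2). That choice needs doses compared beyond the 28-day DLT window, and most exposure after escalation falls there. If later events and responses sit under the starting dose, a low dose can look both more toxic and more active than it was, and experience gained at the higher dose is not visible at that dose.

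**Working it through.** The plan states no figure on this point, so there is none to reproduce. The check is a reading of the rules, then arithmetic to show scale.

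**1. Do the rules cover escalated patients?** The SAP 7.1 sentence concerns dose modification, and the same section glosses that term: "TEAEs leading to dose modification (i.e., dose reduced or dose interrupted) of study treatment". Read alone, it does not clearly reach escalation. SAP 4.3 and 4.4 do, because they place every patient by enrolled or initial dose without exception.

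**2. Are events after escalation counted?** Yes. The TEAE window includes time at the escalated dose. Under the worst-grade rule, a Grade 1 event at 40 mg that becomes Grade 3 at 120 mg is tabulated once, as Grade 3, under 40 mg.

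**3. When can the named step occur?** Taking the Level 1 and Level 2 DLT periods in sequence (28 days each), the earliest day is 28 + 28 + 1 = Day 57. The step is 120/40 = 3-fold.

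**4. How much exposure is involved?** Assume 56 days at 40 mg (56 × 40 = 2,240 mg), then m days at 120 mg. The values of m are assumptions.

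| m (days) | Share of days at 120 mg, m/(56 + m) | Share of mg at 120 mg, 120m/(2,240 + 120m) | Dose intensity against initial dose, (2,240 + 120m)/[40(56 + m)] |
|---|---|---|---|
| 28 | 33% | 3,360/5,600 = 60% | 5,600/3,360 = 167% |
| 56 | 50% | 6,720/8,960 = 75% | 8,960/4,480 = 200% |
| 112 | 67% | 13,440/15,680 = 86% | 15,680/6,720 = 233% |

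In every row, all AEs are tabulated under 40 mg.

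**5. What could the 40 mg column show?** Let q be the Grade 3 or worse risk while on 40 mg, r the further independent risk while on 120 mg, and s the share who escalate. The displayed rate is q + s(1 − q)r. All inputs are assumed.

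- q = 10%, s = 50%, r = 30%: 0.10 + 0.5 × 0.90 × 0.30 = 23.5%
- q = 10%, s = 100%, r = 50%: 0.10 + 0.90 × 0.50 = 55%
- q = 20%, s = 50%, r = 30%: 0.20 + 0.5 × 0.80 × 0.30 = 32%
- q = 20%, s = 100%, r = 50%: 0.20 + 0.80 × 0.50 = 60%
- s = 0: the rate stays at q

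**6. Does anything offset it?** SAP 7.1 plans listings of all TEAEs, Grade 3 or worse TEAEs and serious TEAEs, but does not specify dose at onset for them. The regrouping in SAP 5.1 is optional and pools dose levels. An irinotecan escalation would not show in the FOLFIRI exposure outputs listed in SAP 7.2.

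**The case against.** The strongest defence is that grouping by initial dose is a reasonable main display for a descriptive Phase 1 study and keeps each patient in one column. Other views exist: TEAE and exposure listings, a count of escalated patients, swimmer plots with timing of response, and separate exposure-response work. This stands, and it is why the initial-dose tables should remain. None of these outputs is specified to show dose at onset.

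The defence also limits several stronger readings that a reader might infer.

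- *The SAP 7.1 sentence alone settles the matter.* It does not, given the gloss on dose modification. The rule rests on SAP 4.3, 4.4 and 5.1.
- *The higher dose is made to look less toxic.* Escalated patients are missing from both the numerator and the denominator of that column, which still describes those who started there. What is lost is information on late toxicity. Patients reduced from a high dose keep their later events in the high-dose column, which pushes the other way.
- *By-dose TEAE incidence is the primary endpoint.* The endpoint tables name incidence and severity of TEAEs without specifying by dose.
- *The MTD is compromised.* DLTs count only in the first 28 days, and for Level 1 patients the named step comes later. The Synopsis and SAP give no minimum time at the starting dose for other patients, such as backfill patients whose relevant DLTs count. A misplaced DLT is therefore unlikely but not excluded.
- *One event in two patients, 1/2 = 50%, measures the problem.* That figure reflects a cohort of up to 2 in a study of up to 104.

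**Conclusion.** The concern holds for the by-dose tables. Followed as written, the SAP shows TEAEs that start or worsen after escalation, and responses first documented then, under the lower starting dose, with nothing planned to separate them. Apparent toxicity and activity at the lower dose can be inflated, and late-toxicity experience at the higher dose does not appear at that dose.

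The size cannot be fixed from the documents, because they do not say how many patients will escalate or for how long. If 50% to 100% escalate and the further risk at 120 mg is 30% to 50%, a 10% risk at 40 mg displays as about 24% to 55%, and a 20% risk as 32% to 60%. If nobody escalates, there is no effect. These ranges illustrate scale and are not predictions. The matter bears on the RP2D judgement; the overall safety summary is untouched and the MTD is largely so.

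**What to change.** Keep the initial-dose tables as the main display, and add the following to the SAP:

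- One supplementary summary of TEAEs, Grade 3 or worse TEAEs and SAEs by actual RP-6306 dose at onset, with patient-time at each dose as denominator. For an event that worsens after escalation, define onset of the worsened grade as the date of worsening.
- Irinotecan dose at onset in the AE listing, or in the table where irinotecan was escalated. Crossing both drugs throughout would give sparse cells.
- A flag on AEs and responses first documented after the first intrapatient escalation. Events should not be truncated at escalation, because that would drop events that the TEAE definition includes.
- A statement in SAP 7.1 of whether its attribution sentence is meant to cover escalation, so that it agrees with SAP 4.3 and 4.4.

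This is a cheap improvement: a few extra outputs from dosing dates already collected, and SAP 7.2 already derives the number of days dosed at each RP-6306 level. The downside is that escalated patients contribute to more than one dose column, so the columns are not independent and the table needs a footnote saying so.
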